The Effects of computerized Cognitive Behavior Therapy (cCBT) on Brain Health: A feasibility study

PROTOCOL SUMMARY

Full Title	The Effects of computerized Cognitive Behavior Therapy (cCBT) on Brain Health : A feasibility study
Short title	HIV, depression and cCBT
Sponsor	McGill University
Funding	Canadian Institute of Health Research (CIHR)
Principal Investigators	[name], Department of Psychiatry, McGill University [name], Department of Psychiatry, McGill University [name], Department of Psychology, McGill University
Associate investigators	[name] [name]
Objectives	Among individuals with symptoms of depression and cognitive difficulties, and whose depression is treated with computerized Cognitive Behavioral Therapy (cCBT), to what extent is reduction in depressive symptoms associated with reduced reports of cognitive difficulties. Secondarily, to what extent is the reduction self reported cognitive difficulties concordant with improvement cognitive performance.
Study Population	Inclusion Criteria 
• Participants in the cohort study “Understanding and Optimizing Brain Health in HIV Now” with at least one remaining visit• Able to communicate (understand and read) in English• Depression subscale of the HADS (HADS-D) ≥ 8

The Effects of computerized Cognitive Behavior Therapy (cCBT) on Brain Health: A feasibility study

	
• Presence of self-reported cognitive difficulties (PDQ) ≥ 30• Score on the B-CAM > 14• Willing to undergo 9 sessions of cCBT as per instructions and to have weekly contact with a research coordinator from the central site (by email or phone)• Access to the internet 
Exclusion Criteria
 
• Current use of street drugs (excluding marijuana)
Study Design	Single cohort design with two repeated measures
Sample Size	30 participants have completed the intervention and the final evaluation
Participant involvement	Questionnaires at screening, pre- and post- intervention 9 sessions of cCBT plus regular contacts from the central site

The Effects of computerized Cognitive Behavior Therapy (cCBT) on Brain Health: A feasibility study

BACKGROUND

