- Score on the Patient Deficit Questionnaire (PDQ) [17] ≥ 30
- B-CAM score > 14 to ensure that they can navigate the computer program
- Have not had changes in medication that could potentially interfere with mood and cognition, and are not expected to undergo such changes for the duration of the study
- Have been on a stable HAART regimen for > 6 months
- Willing to participate in cCBT as per instructions and to have regular contacts with the central site
- Have access to the internet
- Have at least one remaining visit in the main cohort study

Exclusion criteria:

- Current use of street drugs (excluding marijuana)

Potentially eligible participants will be identified from the BHN cohort and will be contacted by phone or e-mail (depending on the contact information provided by the participant) by a research coordinator at the central (Montreal) site who will introduce the study. Individuals who consent verbally will be asked to provide their email address. All participants will receive an e-mail with the informed consent document and will be instructed to return the e-mail to confirm consent to participate. Those consenting will be asked to complete on-line questionnaires (HADS and HIV-specific questionnaire of cognitive difficulties, the C3Q [18]) on a secure site to confirm eligibility and collect baseline information. Those remaining eligible will enter the intervention phase. People will be contacted and screened until a maximum of 36 participants have entered the intervention phase. This number was chosen as sample sizes around 30 for analysis are often used in exploratory studies to optimize an analysis based on comparison of means under the central limit theorem [16], and we except some drop outs from the cCBT therapy.

Intervention:

Participants who are eligible will receive online access to the Good Days Ahead cCBT program. Good Days Ahead is a learning module based on scientifically proven, evidence-based techniques. The program's content follows the teachings of the basic principles of CBT. The

The Effects of computerized Cognitive Behavior Therapy (cCBT) on Brain Health: A feasibility study

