underlying platform generates customized learning experiences for each individual user with content including videos, text, quizzes and interactive exercises. The program comprises nine lessons of 30 minute each during which the user first learns the key concepts; then applies them to the program's main character who suffers from depression; and then applies those techniques to their own personal challenges (<http://www.empower-interactive.com/solutions/good-days-ahead>). Participants are expected to complete the nine sessions over 9-12 weeks.

As patients complete the cCBT program, their progress will be monitored by the research coordinator through a secure web site, using the program's dashboard feature that includes tracking of mood ratings, exercises, comprehension and completion rates. Participants will receive guidance during regular contacts by a trained research coordinator knowledgeable about the program and the basics of CBT.

MEASUREMENT

Three types of measures are under study: (i) depressive symptoms, (ii) self-reported cognitive difficulties; (ii) cognitive performance.

(i) Depressive symptoms will be measured using the Hospital Anxiety and Depression Scale (HADS) [19] before beginning and right after cCBT completion. It comprises two 7-item scales designed to rate depression and anxiety. It was developed to be brief, non-threatening and to exclude items which might reflect somatic symptoms. It has been widely used in research [20]. A score on the depression subscale (HADS-D) ≥ 8 is indicative of the presence of depression.

(ii) Self-reported cognitive difficulties will be measured using the C3Q collected before beginning and right after cCBT completion. The C3Q is a self-report measure of cognitive difficulties comprised of 18 items covering multiple cognitive domains. For each item, individuals rate the frequency of a cognitive difficulty on a three-point scale. The items fit the Rasch model, producing a legitimate total score with mathematical properties ranging from 0-36 with lower scores indicating more severe difficulties. C3Q has good content and construct validity and a good internal reliability (Person Separation Index 0.84) [18]. The mean score of C3Q among HIV+ individuals is 26.3 (SD: 8.2).

(iii) Cognitive performance will be measured by the B-CAM, a computerized test of cognition that yields a score on a continuous metric [21]. The B-CAM is administered at the regular BHN

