The Effects of computerized Cognitive Behavior Therapy (cCBT) on Brain Health: A feasibility study

cohort visits. Two values will be used, those closest to the beginning and end of the CBT intervention period, usually 9 months apart.

STATISTICAL ANALYSIS AND SAMPLE SIZE

Basic descriptive statistics will be used to characterize the participants including values on all the outcomes.

To meet the first aim of linking change in depressive symptoms (as a result of cCBT) to change in self-reported cognitive difficulties, an analysis based on a comparison of two means will be carried out. The cCBT cohort will be classified as having changed on depressive symptoms if the score on the HADS-D has either fallen to below 8 or decreased by $\frac{1}{2}$ SD (2 points). The mean value of change on the C3Q will be compared between these two groups (depression improved vs no change), using an adjusted t-test based on linear regression, adjusted for covariates that differ between the two groups. This t-test is an estimate of between group effect size. The parameter of interest, however, is the within group effect size for cognitive change using the standardized response mean (SRM), which is the average within group change divided by the standard deviation of change. The two SRMs will be compared using relative effectiveness: SRM (depression improved group) / SRM (depression no change group)[16]. If this ratio exceeds 1.0, there is supportive evidence for a greater response in the depression improved group. This information on the between and within-effect sizes will be used to develop a fully powered study of this association.

The extent to which changes in self-reports are concordant with changes in cognitive performance will be assessed using percent agreement and 95% confidence intervals (CI). Each person will be classified as a responder or not based on change on the C3Q and on the B-CAM, with responder status defined as improvement of $\frac{1}{2}$ SD. This represents a change of 4 points on the C3Q and 2.3 points for the B-CAM. The table below shows the potential outcome patterns. If the value of c=0, all persons with decreased reports of cognitive difficulties also had improved cognitive performance with cCBT.

The Effects of computerized Cognitive Behavior Therapy (cCBT) on Brain Health: A feasibility study

		Cognitive difficulties C3Q	
		Decreased	no change
Cognitive performance B-CAM	improved	a	b
	no change	c	d

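### Choosing covariates by whether they differ between about 30 self-formed responders and non-responders lets chance decide whether the C3Q estimate is raw or baseline-adjusted

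*Combined protocol and SAP*

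**What the plan says.** Under Statistical Analysis and Sample Size, participants count as improved "if the score on the HADS-D has either fallen to below 8 or decreased by" half an SD, given as 2 points. Then: "The mean value of change on the C3Q will be compared between these two groups (depression improved vs no change)". The method is a t-test from a linear regression, "adjusted for covariates that differ between the two groups".

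That is the whole covariate rule. Nothing in the document lists candidate covariates, says what counts as a difference, or puts a baseline score in the model regardless. Both baseline scores are available: the Measurement section has HADS and C3Q collected before cCBT and again right after it.

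The same section calls this regression an estimate of the between-group effect size and names the within-group SRM as the parameter of interest. Both kinds of effect size are to feed the design of a fully powered study. On numbers, the Protocol Summary gives "30 participants have completed the intervention and the final evaluation", and recruitment runs "until a maximum of 36 participants have entered the intervention phase".

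**The concern.** The fault lies in a rule the plan states, not only in a missing list. Whether a covariate confounds the comparison depends on how it relates to group membership and to C3Q change. Whether a difference shows up in about 30 people is a weak signal of either.

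Two covariates matter on their face. Baseline HADS-D enters the definition of the groups: entry requires 8 or more, so someone entering at 8 is improved after a 1-point fall, while anyone entering higher needs 2. Baseline C3Q bears on C3Q change through regression to the mean. Some imbalance may therefore be systematic, and failing to detect it does not make omission safe.

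At stake is what the coefficient means. In one realisation of the study it would be a raw difference in change, in another a baseline-adjusted one. That is a poor input for planning a later trial, and a reader could not tell whether the covariates were settled before the results were seen.

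**Working it through.** **Figures in the plan.** There is no power or precision calculation for the C3Q comparison to reproduce. The relevant scale is the C3Q SD: "The mean score of C3Q among HIV+ individuals is 26.3 (SD: 8.2)". Half of it is 8.2/2 = 4.1, which matches the stated responder threshold: "This represents a change of 4 points on the C3Q and 2.3 points for the B-CAM".

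**1. How large must a difference be to be noticed?** Take *differ* to mean p<0.05 in a two-sample t-test (an assumption) with 30 analysed, so 28 degrees of freedom and a critical value of 2.048. The smallest flagged difference in SD units is 2.048 × √(1/n₁ + 1/n₂). The last column is the noncentral-t probability that a true 0.5 SD imbalance is not flagged.

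| Split | √(1/n₁+1/n₂) | Smallest flagged, SD | On C3Q (× 8.2) | 0.5 SD missed |
|---|---|---|---|---|
| 15/15 | 0.365 | 0.75 | 6.1 | 74% |
| 20/10 | 0.387 | 0.79 | 6.5 | 76% |
| 24/6 | 0.456 | 0.93 | 7.7 | 82% |

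A baseline C3Q gap must therefore exceed the plan's own 4-point responder change before it is adjusted for. Looser screens help only in part: the 0.5 SD imbalance is missed 62 to 71% of the time at p<0.10 and 47 to 57% at p<0.20. If *differ* means an observed standardised difference above 0.25, a covariate with a true 0.3 SD imbalance is still left out 34 to 38% of the time.

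**2. What does omission do in one dataset?** Leaving out baseline C3Q shifts the change-score difference, relative to the baseline-adjusted one, by (1 − pre-post correlation) × imbalance. For an unflagged 4-point gap this is 0.3 × 4 = 1.2 points at correlation 0.7 and 0.5 × 4 = 2.0 points at 0.5.

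**3. Simulation with the plan's grouping rule.** Cohorts of 30 were grouped by HADS-D below 8 or a 2-point fall. Assumptions beyond the document: HADS-D SD 4 (implied by half an SD being 2), pre-post correlations 0.5 to 0.7, baseline HADS-D/C3Q correlation 0 to −0.4, average HADS-D fall 0 to 1.5, and a p<0.05 screen.

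- Baseline HADS-D was left out in 83 to 94% of cohorts, baseline C3Q in 94 to 95%, and both in 78 to 90%. A separate simulation under the same grouping rule gave about 70 to 78% for both, so roughly 70 to 90% is a fair range.
- The screened and always-adjusted estimates differed by a median of 0.5 to 1.0 C3Q points, and by more than 1 point in 25 to 50% of cohorts.
- The standard error was smaller with fixed adjustment in every scenario: at the least 2.31 to 2.22 (1 − 2.22/2.31 = 4% smaller), at the most 2.85 to 2.50 (1 − 2.50/2.85 = 12% smaller). Expressed the other way, the screened model's standard error is about 4 to 14% larger.
- Averaged over cohorts, screened minus always-adjusted was within about 0.2 points.
- In one scenario at p<0.20, both baselines were still left out in 56% of cohorts, and the estimates were more than 1 point apart in 24%.

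**The case against.** The strongest objection is that always fitting the baseline is not automatically right when the groups form themselves. Suppose C3Q does not truly change, regression to the mean is pure measurement error, and the improved group truly starts 0.5 SD lower. With the stated reliability index of 0.84, the slope of change on baseline is −(1 − 0.84) = −0.16. The adjusted difference is then biased by −0.16 × (0.5 × 8.2) = −0.66 points. In simulation at 15/15, raw change had bias 0.00, the plan's rule −0.33 and fixed adjustment −0.66, with root mean square error 1.84 for fixed adjustment against 1.69 for raw change. This is Lord's paradox, and it stands. It does not rescue the screening rule, which only mixes the two answers according to chance, but it means the adjusted model's assumption must be stated and the raw result shown beside it.

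A reader might go further and infer that the rule leaves material confounding, 0.3 to 1.05 C3Q points, which fixed adjustment would remove. The document does not support that. Those figures need an imposed 0.5 SD baseline C3Q imbalance, a p<0.05 screen, and a model in which change depends on the observed baseline at slopes of −0.16 to −0.5. Nothing in the plan says the groups will differ that much on C3Q, and under its own grouping rule the average shift is about 0.2 points.

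Two further points are fair. The plan never defines *differ*, so every omission rate is conditional on a screen it does not state. And the study is openly exploratory, with the SRM as its parameter of interest. The first is why a range of screens is shown. The second lowers the stakes but does not remove them, because the between-group estimate is also meant to inform the later study.

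**Conclusion.** The point holds in a limited form. The covariate rule is an unreliable guide to confounding at this size, and it lets the data decide whether the reported difference is raw or baseline-adjusted. Under a p<0.05 screen, a true 0.5 SD imbalance is missed 74 to 82% of the time, both baselines are usually omitted, and the choice moves the estimate by more than 1 C3Q point in about a quarter to a half of simulated cohorts. Against a 4-point responder change, that is instability worth removing.

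The harm is an unstable estimand with a modest loss of precision, not a demonstrated large bias. The omission rates are firm given the screen and the split; the size of the shifts depends on the assumed correlations, HADS-D SD and average fall. It would also be wrong to infer that the SRM ratio is affected or repaired: it is described without any adjustment. Nor does this point argue for replacing the two groups by continuous HADS-D change.

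**What to change.** Keep the improved / no-change comparison and replace the covariate phrase by:

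> adjusted for baseline C3Q and baseline HADS-D, included whatever the observed group differences

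Then add that the unadjusted difference in C3Q change, and any model with further covariates, are reported as labelled sensitivity analyses. State the assumption behind the main model: without improvement in depression, participants with the same baseline scores would be expected to change alike on C3Q in both groups. If the raw and adjusted results disagree, report that disagreement to whoever plans the next study.

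Cost: two or three sentences and no new data, since both baselines are already collected. The two extra terms take residual degrees of freedom from 28 to 26 at 30 analysed, and in the scenarios examined the standard error still fell. The SRM ratio remains unadjusted and would need separate attention.

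### The plan adjusts the between-group t-test but not the SRM ratio that it names as its parameter of interest, so baseline differences can move that ratio either way with no true link

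*Combined protocol and SAP*

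**What the plan says.** All of this is in the STATISTICAL ANALYSIS AND SAMPLE SIZE section unless another section is named.

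- **Groups.** Participants are split after treatment. A person counts as improved if the HADS-D score "has either fallen to below 8 or decreased by" half an SD, given as 2 points. Nothing balances the two groups at entry.
- **Between-group comparison.** Mean C3Q change is compared "using an adjusted t-test based on linear regression, adjusted for covariates that differ between the two groups". Baseline C3Q is not named as a covariate.
- **Preferred quantity.** "The parameter of interest, however, is the within group effect size for cognitive change using the standardized response mean (SRM". It is defined as a mean, "which is the average within group change divided by the standard deviation of change", with no covariate term.
- **Reading rule.** The two SRMs are compared as "SRM (depression improved group) / SRM (depression no change group", and "If this ratio exceeds 1.0, there is supportive evidence for a greater response in the depression improved group". No confidence interval or test is given for the ratio.
- **Use.** Both the between-group and the within-group effect sizes are to inform the design of a later, powered study.
- **Scale (MEASUREMENT).** "The mean score of C3Q among HIV+ individuals is 26.3 (SD: 8.2". The C3Q total is described as "ranging from 0-36 with lower scores indicating more severe difficulties", so a rise is an improvement.

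**The concern.** By adjusting the t-test, the plan accepts that the HADS-D groups may differ in ways that affect C3Q change. It then moves its interest to a quantity built from unadjusted changes. This is separate from the choice of covariates: with a complete, pre-specified list, the SRM ratio as written would still be raw.

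Baseline C3Q is the clearest example. Where the pre-post correlation is below 1, people who start low tend to gain more on retest. If the improved group happens to start lower, its raw gain is inflated and the ratio can exceed 1.0 with no link between mood change and cognitive change. If it starts higher, a real link can be hidden. The adjusted t-test and the raw ratio can then point in different directions. The plan does not say how to read them in that case, and both feed the next study's design.

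**Working it through.** **The plan's own figures.** The plan gives no expected SRM, SRM ratio, baseline gap, correlation or mean gain for this aim. The one related figure, half an SD on the C3Q, reproduces: 8.2/2 = 4.1, which the plan rounds to 4.

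**Inputs.** From the documents: SD 8.2, and 30 analysed. Assumed, not in the documents: baseline gap g (improved group lower by 2 to 4.1 points), pre-post correlation r (0.5 to 0.8), gain m common to both groups (2 to 4.1 points), equal SDs, no link between HADS-D change and C3Q change, and group sizes from 15/15 to 20/10.

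**Model.** If both groups regress towards one common mean:

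- expected raw gain, improved group: m + (1 − r)g/2
- expected raw gain, no-change group: m − (1 − r)g/2
- SD of change in either group: 8.2 × √(2(1 − r))

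The SD of change cancels, so the ratio of expected SRMs is [m + (1 − r)g/2] / [m − (1 − r)g/2].

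**One worked case: g = 4.1, r = 0.6, m = 3.**

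- (1 − 0.6) × 4.1 = 1.64 points of spurious difference, 0.82 on each side
- SD of change = 8.2 × √0.8 = 7.33
- SRMs: 3.82/7.33 = 0.52 and 2.18/7.33 = 0.30
- ratio = 3.82/2.18 = 1.75

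**Range of the ratio over the assumptions.**

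| Gap | Common gain | r = 0.5 | r = 0.6 | r = 0.7 | r = 0.8 |
|---|---|---|---|---|---|
| 4.1 | 2 | 3.10 | 2.39 | 1.89 | 1.52 |
| 4.1 | 3 | 2.04 | 1.75 | 1.52 | 1.32 |
| 4.1 | 4.1 | 1.67 | 1.50 | 1.35 | 1.22 |
| 2 | 2 | 1.67 | 1.50 | 1.35 | 1.22 |
| 2 | 3 | 1.40 | 1.31 | 1.22 | 1.14 |
| 2 | 4.1 | 1.28 | 1.22 | 1.16 | 1.10 |

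Reversing the gap gives the reciprocals, 0.32 to 0.91. With r = 1 or no gap, the ratio is 1.

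**How often a gap this large arises by chance.** The standard error of the baseline difference is 8.2 × √(1/n₁ + 1/n₂): 2.99 for 15/15 and 3.18 for 20/10. A gap of at least 4.1 points in either direction has probability 0.17 and 0.20. Half of that, about 8.5% to 10%, is in the direction that inflates the ratio.

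**Effect of adjusting under this model.** At a common baseline C3Q both groups' adjusted gain is m, so the ratio of expected adjusted SRMs is 1.00. In simulated studies of 15 per group with g = 4.1, r = 0.7 and m = 4.1, the raw ratio exceeded 1.0 in 67% and the adjusted ratio in 50%. With no gap, both did so in 49%. With no imposed gap, r = 0.6 and m = 3, raw and adjusted ratios fell on opposite sides of 1.0 in about 16% of studies (10% to 18% for r from 0.8 to 0.5).

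**The same case under a different model.** Suppose each group has its own stable C3Q level and regresses to that. With g = 4.1, r = 0.6 and m = 3, raw gains are 3 and 3, and the raw ratio is 1.00. Adjusting to a common baseline gives 3 − 0.4 × 2.05 = 2.18 for the improved group and 3 + 0.82 = 3.82 for the other. That is a false difference of −1.64 points and a false ratio of 2.18/3.82 = 0.57.

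**The case against.** The strongest objection is that the remedy can create the bias it is meant to remove. Baseline adjustment is right for a chance gap. If the groups differ stably at entry, raw changes are unbiased and adjusted ones are not, as the last step of the working shows. This is Lord's paradox, and the documents do not say which model applies. The objection stands: adjustment cannot be presented as an unconditional correction.

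Three further points also stand in part.

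- **Noise.** With no systematic gap and 15 per group (r = 0.6, m = 3), the central 95% range of the ratio is roughly −5 to 9 whether raw or adjusted. Chance imbalance is already part of that spread. An unstable ratio read against 1.0 with no interval is at least as large a weakness, and adjustment does not cure it.
- **SD.** The 8.2 is given for HIV+ individuals generally. Entrants are selected on PDQ and HADS-D, so theirs may differ. With an assumed SD of 6, the chance of a 4.1-point gap in either direction is 6% to 8%.
- **Purpose.** STUDY DESIGN presents the study as exploratory, and the adjusted t-test is reported too.

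A reader might infer that a baseline gap by itself yields a ratio near 1.75. The documents do not support that: the value also needs an assumed correlation, an assumed common gain and a gap in one direction. A reader might also infer that the raw ratio alone settles the first aim. The plan claims only supportive evidence and carries both effect sizes forward.

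**Conclusion.** The point holds as a mismatch within the plan. The plan treats adjustment as needed between these groups, but leaves it out of the quantity it prefers and interprets, and no other section repairs this. The possible shift is material: expected ratios of about 1.1 to 3.1 with no true link, or 0.32 to 0.91 with the gap reversed. These figures rest on the assumed gap, correlation and common gain, and on both groups regressing to one mean. They illustrate what could happen and do not predict this study's result. The working does not show that the ratio is biased upwards, or that the adjusted ratio is the correct one. It supports showing both and tying the reading rule to their agreement. Because the study is exploratory and the t-test is already adjusted, this is a change worth making rather than a fault that undermines the study.

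**What to change.** In STATISTICAL ANALYSIS AND SAMPLE SIZE:

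1. Name baseline C3Q as a covariate in the planned regression, whether or not it is judged to differ between the groups.
2. From that model take each group's adjusted mean change at the overall covariate mean, and divide it by that group's SD of change.
3. Report this adjusted SRM comparison together with the raw one, each labelled as such.
4. Call the evidence supportive only if both agree, and say that disagreement will be reported as inconclusive.
5. State the limits: baseline adjustment assumes that both groups regress to a common mean and can mislead if their C3Q levels are stably different; and neither version removes the sampling noise of the ratio at about 30 participants.

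The cost is analysis wording. The regression is already planned, with baseline C3Q as one added term, and C3Q is already collected before and after cCBT. No visit, sample size or data collection changes.

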Among individuals with symptoms of depression who report cognitive difficulties and whose

The Effects of computerized Cognitive Behavior Therapy (cCBT) on Brain Health: A feasibility study

depression is treated with computerized Cognitive Behavioral Therapy (cCBT), to what extent is reduction in depressive symptoms associated with reduced reports of cognitive difficulties?

Secondarily, to what extent is the reduction in self-reported cognitive difficulties concordant with improvement cognitive performance?

STUDY HYPOTHESIS

The hypothesis is that people whose depressive symptoms are reduced following treatment with cCBT will also report fewer cognitive difficulties than before treatment. A second hypothesis is that changes in self-reported cognition will be concordant with changes in cognitive performance, such that people who make no improvement in self-report cognition will also show no improvement in cognitive performance and those who do improve on self-report will improve on cognitive performance.

STUDY DESIGN

This study is part of a larger project based upon a cohort multiple randomized controlled design [1]. Within a fully characterized cohort followed over time (n=840), people meeting the specific criteria for one or more interventions (here cCBT) are identified and a sample is randomly selected to receive the intervention. When the intervention is under investigation, the remaining eligible persons who do not receive the intervention serve as controls. In this study, we are not testing the effectiveness of cCBT as this has been demonstrated. Rather we are focusing on changes in cognition in relation to depressive symptoms mediated by cCBT. This study is an exploration of a hypothesis using a single cohort design with two repeated measures. For exploratory studies, an N of 30 optimizes an analysis based on means under the central limit theorem [16] .

POPULATION

Individuals who report depressive symptoms and self-reports of cognitive difficulties and who have agreed to be contacted for sub-studies will be invited to participate.

Inclusion criteria:

- Participant in the *Understanding and Optimizing Brain Health in HIV Now* (BHN) study

The Effects of computerized Cognitive Behavior Therapy (cCBT) on Brain Health: A feasibility study

- Able to communicate (understand and read) in English (Good Days Ahead software is only available in English)
- Score on the Hospital Anxiety and Depression Scale- depression subscale (HADS-D) ≥ 8

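### The SRM-ratio criterion (above 1.0 is supportive) has no sign condition and no interval, so it can misread the result when the no-change group's SRM is near zero or negative

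*Combined protocol and SAP*

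**What the plan says.** Under Statistical Analysis and Sample Size, participants are split by whether HADS-D improved. Mean C3Q change is compared between the two groups "using an adjusted t-test based on linear regression, adjusted for covariates that differ between the two groups", and the plan adds: "This t-test is an estimate of between group effect size".

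It then gives priority to a different quantity: "The parameter of interest, however, is the within group effect size for cognitive change using the standardized response mean (SRM"), defined as mean change divided by the SD of change. The comparison of groups is set out as follows: "The two SRMs will be compared using relative effectiveness: SRM (depression improved group) / SRM (depression no change group"). The reading is: "If this ratio exceeds 1.0, there is supportive evidence for a greater response in the depression improved group".

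The section sets no condition on the sign of either SRM and makes no provision for a zero or negative denominator. It plans no interval for the SRMs or their ratio. The one interval it plans is for the second aim, where concordance "will be assessed using percent agreement and 95% confidence intervals (CI").

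Two other places bear on the point. The Study Hypothesis section predicts that "people whose depressive symptoms are reduced following treatment with cCBT will also report fewer cognitive difficulties than before treatment"; it predicts nothing about C3Q in people whose depression does not improve. The Measurement section fixes the direction of the C3Q, "ranging from 0-36 with lower scores indicating more severe difficulties", so a positive change (after minus before) is a gain.

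**The concern.** A ratio of two signed quantities orders them correctly only when the denominator is positive. Here the denominator is the SRM of the group for which no gain is predicted. That group also takes in anyone whose depression worsened, since it holds everyone who fails the HADS-D improvement criterion. A value near zero or below is therefore realistic, and it is one form that a strong association between depression and self-reported cognition would take.

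Three things can go wrong:

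- If the no-change SRM is close to zero, the ratio is unstable in both size and sign.
- If the no-change group worsens while the improved group gains, the ratio is negative and the criterion is not met.
- If both groups worsen and the improved group worsens more, the ratio can exceed 1 and the criterion is met.

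Redefining change as before minus after does not help. Both signs flip and the ratio is unchanged, so it cannot separate two groups that both improved from two that both worsened.

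This matters because the SRM is the declared parameter of interest, the 1.0 threshold is the only one given for comparing the two SRMs, and the effect sizes are meant to feed the design of a fully powered study.

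**Working it through.** The plan states no expected ratio, power or error rate for this rule, so there is no figure of its own to reproduce.

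**Inputs from the plan.** N = 30 analysed; SRM = mean change / SD of change; ratio = SRM(improved) / SRM(no change); criterion: ratio > 1.0; C3Q SD 8.2.

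**Inputs assumed.** The documents do not give the group split or the true SRMs. The simulation also assumes normal change scores, equal SDs and independent groups.

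**Step 1. Arithmetic on the rule, with no assumption about true effects.**

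| SRM improved | SRM no change | Ratio | Criterion met? | Improved group's SRM larger? |
|---|---|---|---|---|
| 0.5 | -0.2 | -2.5 | no | yes, by 0.7 |
| -0.4 | -0.2 | 2.0 | yes | no, lower by 0.2 |
| -0.2 | -0.4 | 0.5 | no | yes, by 0.2 |
| 0.5 | 0.01 | 50 | yes | yes, by 0.49 |
| 0.5 | -0.01 | -50 | no | yes, by 0.51 |

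The last two rows are practically the same data.

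**Step 2. When is the denominator's sign settled?** The 95% t interval for the no-change mean excludes zero only if the observed SRM exceeds t(0.975, n-1)/sqrt(n) in size:

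- n = 15: 2.145/sqrt(15) = 0.55
- n = 10: 2.262/sqrt(10) = 0.72
- n = 6: 2.571/sqrt(6) = 1.05

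**Step 3. Simulation, 200,000 replicates per scenario, split 15/15.**

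| True SRMs (improved vs no change) | Criterion met | Not met although improved group's sample SRM is larger |
|---|---|---|
| 1.0 vs 0.5 | 86% | 3% |
| 0.8 vs 0.4 | 78% | 6% |
| 0.8 vs 0.2 | 72% | 22% |
| 0.8 vs 0 | 48% | 50% |
| 0.8 vs -0.2 | 22% | 78% |

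The improved group has the larger sample SRM in 94% of replicates at 0.8 vs 0.2, 98% at 0.8 vs 0, and 99.6% at 0.8 vs -0.2. As the true contrast grows, the criterion is met less often. At 0.8 vs 0 the central 95% of ratios runs from about -52 to +52.

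When both groups worsen (-0.5 vs -0.2), the criterion is met in 57% of replicates, almost always with the improved group's SRM the lower one.

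**Step 4. Other splits.** For 20/10, 10/20 and 24/6 (improved/no change), the criterion is met in 47%, 48% and 44% at 0.8 vs 0, and in 66%, 75% and 55% at 0.8 vs 0.2.

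**Step 5. No association.** With equal true SRMs the criterion is met in between 14% (both 0, 24/6) and 51% (both 0.8, 10/20) of replicates. About 50% is what any directional point estimate gives, so at the upper end the gap is the missing interval.

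**The case against.** The best reply is that the plan only says what a ratio above 1.0 supports and is silent at 1.0 or below. A negative ratio then yields no stated wrong conclusion, and an analyst who has computed both SRMs will see their signs. The outright wrong reading, support when the improved group did worse, needs both sample SRMs to be negative. It occurs in about 1% of replicates or fewer in the scenarios run with an improved-group true SRM of 0.5 to 1.0. Everyone receives the program and was selected for high symptom scores, so some gain in the no-change group is plausible. With a no-change SRM of 0.4 to 0.5, the miss rate is only 3 to 6% at 15/15. The study is exploratory, the adjusted comparison sits in the same paragraph, and the cited reference for relative effectiveness may carry a sign convention that cannot be seen here.

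Much of this limits the harm, and it is accepted as such. It does not rescue the criterion. A stated criterion that fails when the result most favours the hypothesis is still a poor one. No sign convention for change can cure a ratio that is the same for two gains and two losses. The regression does give the direction, but the plan ranks the SRM above it and says nothing about what to do if the two disagree.

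A sign condition with intervals would be a lesser repair. It would leave no comparison whenever the condition failed, and by Step 2 an observed no-change SRM of up to about 0.55 leaves the sign open at n = 15. Two remarks on the remedy are fair: the standardiser for Hedges' g should be named, and an interval adjusted for covariates chosen because they differ between groups depends on that choice.

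**Conclusion.** The concern holds and should be fixed. That the criterion can give the wrong direction is a matter of arithmetic and rests on no assumption. How often it would do so depends on the unknown true SRMs and group split. At 15/15 it fails to credit a larger improved-group SRM in about 50% of replicates if the no-change SRM is truly 0, and in about 78% if it is -0.2. That falls to 22% at 0.2 and to 3 to 6% at 0.4 to 0.5 (improved-group SRM 0.8, or 1.0 in the last case). When both SRMs are clearly positive the ratio points the right way, and the defect is then the absence of any statement of precision.

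The consequence is moderate: the study explores a hypothesis, and the correct reading can be recovered from the planned regression. The remark that the t-test estimates an effect size is a minor wording fault, since a t statistic grows with sample size.

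**What to change.** - Delete the criterion that a ratio above 1.0 is supportive.
- Base the between-group comparison on the adjusted difference in mean C3Q change (improved minus no change, in points) from the regression already planned, with its 95% CI. Report the unadjusted difference beside it, because the covariates are chosen from the data.
- Report Hedges' g with a 95% CI, standardised by the pooled SD of change. Refer to the adjusted difference and g where the plan now calls the t-test an effect size.
- Keep each group's SRM, with a 95% CI, as the within-group effect size.
- Treat any difference between the SRMs as descriptive, with a CI. Unequal SDs distort it as they do the ratio: a mean gain of 4 with SD 8 gives 4/8 = 0.50, and 2.5 with SD 4 gives 2.5/4 = 0.625. The SRMs then favour the second group although the first gained 1.5 points more.

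C3Q scoring needs no change. The cost is analysis text and a few lines of code, with no new data or participants. The conclusion becomes an estimate with a wide interval. The unadjusted half-width is t(0.975, 28) × sqrt(1/n1 + 1/n0), in SDs of change: 2.048 × sqrt(2/15) = 0.75 at 15/15, 0.79 at 20/10 and 0.93 at 24/6. At 15/15, with an assumed SD of change of 4 to 8.2 points, that is about 3.0 to 6.1 C3Q points. That width shows how little 30 participants can settle, which the design of the next study needs to take into account.
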